8.5.3 Determination of the humoral and cellular immunity

8.5.3.1 Determination of serum antibodies against vaccination antigens

For the evaluation of antibody levels, both NT and enzyme linked immunosorbent assay (ELISA) will be performed [23]. Virus neutralization titers will be defined as the reciprocal of the serum dilution that gives a 90% reduction of virus growth compared to the control without antibody.

Neutralizing antibodies have been shown to be protective [24] and are generally viewed as a surrogate parameter of protection against TBE [17]. Neutralization tests will be performed by PFIZER. Blood samples will be also screened for TBE antibodies by ELISA [23] and will be considered seropositive when the values are above the cut-off of the assay.

8.5.3.2 Determination of cellular immune response

To investigate cellular immunity following TBE vaccination, lymphocyte proliferation and cytokine detection assays will be used. Peripheral blood mononuclear cells (PBMCs) will be isolated from heparinized venous blood by ficoll-diatrizoate centrifugation at 3 points in time as specified above (study visit 1, 3 and 7) and will be cryopreserved and stored in liquid nitrogen for later use. Lymphocyte proliferation will be analysed by [3H]thymidine incorporation and carboxyfluorescein diacetate succinimidyl ester (CFSE) labelling. PBMCs from defined time points for each subject will be thawed [25] and assayed together. As antigen to stimulate PBMCs we will use the whole aluminium hydroxide-free and human albuminfree TBE antigen at 4.8 µg/ml provided by PFIZER. Phytohemagglutinin (PHA) will be used for nonspecifically mitogenic stimulation of PBMCs at either 1 or 5 µg/ml. PBMCs will be cultured in triplicate (10⁵ PBMC/well) with or without various stimuli at 37°C in a CO2 incubator for 6 days before harvesting. For the [3H]thymidine incorporation assay, PBMCs will be then pulsed with radioactive 3H (tritiated) thymidine for sixteen hours. The amount of radioactivity incorporated into DNA in each well will be measured in a scintillation counter and is proportional to the number of proliferating cells, which in turn is a function of the number of lymphocytes that were stimulated by a given antigen to enter the proliferative response. Results will be expressed as Δcpm (calculated as mean counts per minute of stimulated cell cultures minus mean counts per minute of medium control cell cultures) and as the stimulation index (SI), calculated as the ratio of the mean counts per minute of stimulated cell cultures to the mean counts per minute of medium control cell cultures [26]. For the CFSE proliferation assay, PBMCs will be CFSE-loaded (and fluorescein isothiocyanate-labeled) and cultured with medium alone (negative control), or PHA, or the whole aluminium hydroxide-free and human albumin-free TBE antigen at 4.8 µg/ml. After 6

days of incubation at 37°C and 5%CO2, collected cells will be stained with anti-CD3 monoclonal antibody (allophycocyanin), anti-CD8 (peridinin chlorophyll protein), and anti-CD4 (phycoerythrin). A total of 100,000 events in a lymphocyte gate will be analyzed by flow cytometry. Percentages of CD3+, CD8+, and CD4+ CFSE proliferating cells will be evaluated simultaneously by gating on CD3+ T cells and measuring sequentially proliferating CD8+ and CD4+ subsets within the CD3+ subsets. Net percentages of CFSE will be calculated by subtracting the negative control values as described previously [27]. Furthermore, cytokines will be measured in the supernatant (IL-2, IFN-gamma, IL-6, IL-10, TNFalpha) after in vitro stimulation with and without TBE virus antigen or PHA for 48 hours using ELISA.

8.5.3.3 Determination of immune reconstitution in HSCT recipients

The status of immune reconstitution in HSCT recipients prior to and after vaccination will be assessed by immunofluorescence staining of peripheral blood (PB) T and B lymphocytes and flow cytometric analyses. Therefore, PB cells will be stained with monoclonal antibodies and analyzed by FACS for the following cell populations: T lymphocytes (CD3+), B lymphocytes (CD19+), T helper cells (CD3+CD4+), T suppressor cells (CD3+CD8+), natural killer cells (CD3-CD16&56+) and cytotoxic cells (CD3+CD16&56+).

In addition, serum immunoglobulin levels will be analysed. Immune reconstitution and serum immunoglobulin levels will be determined in all HSCT patients prior to the first and third vaccination and 12 weeks after the first vaccination (study visits 1, 5 and 6).

8.5.4 Study endpoints

8.5.4.1 Primary study endpoint

To assess the humoral immunogenicity of the TBE vaccination, the outcome of NT will be analysed four weeks after the second vaccination. Therefore, the number of subjects with NT titers against TBE virus >10, assumed to be the threshold for antibody-mediated protection, will be evaluated.

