TOLERABILITY / SAFETY	Number of subjects with systemic reactions after vaccination
PHARMACOKINETIC /	Νο
PHARMACODYNAMIC	
QUALITY OF LIFE /	No
PHARMACOECONOMIC	
ENDPOINTS	
STATISTICAL METHODOLOGY	Primary Endpoint
	To assess humoral immunogenicity of the TBE vaccination in
	allogeneic HSCT recipients compared to healthy volunteers without
	previous TBE vaccination, the outcome of the neutralilzation test (NT)
	will be assessed four weeks after the second vaccination. Therefore,
	the number of subjects with NT titers against TBE virus >10
	(=seroconversion rate), assumed to be the threshold for antibody-
	mediated protection, will be evaluated.
	Null and alternative hypotheses:
	H ₀ : There is no statistical difference in the seroconversion rate between
	the study population and the control group
	H ₁ : There is statistical difference in the seroconverion rate between the
	study population and the control group
	Type-I and -II errors – power:
	Alpha 0.05. Power 0.8.
	Sample size calculation
	The calculation of the sample size was performed using nQuery 6.1. The primary endpoint is the outcome of the NT against 4 weeks after
	the second vaccination (positive test: Yes/No). Because of deviation of the antibody concentrations from normal distribution (NT level <=10 not detectable indicating a negative test), the outcome is reduced to a binary but clinically more relevant outcome (seroconversion rate: NT
	levels >10 indicates a positive test). Previously, in a study with heart transplant recipients a seroconversion rate of 35% was detected compared to 100% in the healthy control group. In our study we expect
	a seroconversion rate of at least 90% in the healthy control group. In the HSCT patients we expect a seroconversion not exceeding 50%. The
	calculation of the sample size was performed using the following assumption: Significance level alpha 0.05, Power 0.8, ratio of HSC1
	patients/healthy volunteers: 1/1. With a total number of 46 participants (23 HSCT patients and 23 healthy volunteers) the assumed
	difference in the seroconversion rate between groups can be detected (using a two-sided Fisher's Exact Test) with 80% Power. We added 10%
	to adjust for potential loss-to-follow-up which results in 26 HSCT patients and 26 healthy volunteers.

Statistical methodology

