7. STUDY DESIGN

A prospective open-label phase II pilot study will be performed. A total of 52 adult male or female subjects, 26 HSCT patients (study population) and 26 healthy volunteers (control group), will be enrolled in this clinical trial. Eight study visits per patient will be planed. Eligible patients will receive at least two TBE vaccinations (study visit 1 – day 0, study visit 2 -1month after the first vaccination) with a total of two doses of the TBE vaccine FSME IMMUN®. Whenever possible, the patients will receive complete primary vaccination with a third dose of TBE vaccine FSME IMMUN® (study visit 9 - 12 months after the first vaccine will be injected intramuscularly in the Musculus deltoideus.

FSME IMMUN® contains formalin-inactivated TBE virus. One dose (0.5 ml) contains 2.4 µg of antigen inactivated by formaldehyde. Human albumin is used as stabilizer and aluminium hydroxide is used as adjuvant. The vaccine contains traces of formaldehyde, protamine sulphate, neomycin and gentamicin.

Serum samples for determination of antibody levels will be obtained immediately before the first (study visit 1), 4 weeks after the second vaccination (study visit 4), and four weeks after the third vaccination (study visit 8). Blood samples for the analysis of cellular immunity will be taken before the first (study visit 1), one week after the second vaccination (study visit 3) and one week after the third vaccination (study visit 7). Blood samples for determination of the immune reconstitution and the quantitative immunoglobulin levels will be obtained prior to the first (study visit 1) and third vaccination (study visit 6) and 12 weeks after the first vaccination (study visit 5) in HSCT recipients only.

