8.5.2 Study visits

8.5.2.1 Visit 0/ Screening investigation (Day -28)

The investigator will inform the subject about the procedures, risks and benefits oft he study. Fully informed, written consent must be obtained from each subject prior to any assessment being performed. It is important that the subject is allowed sufficient time to consider his/her participation in the study.

The following assessments will be performed:

- Inclusion and exclusion criteria.
- Demographic data including sex, age, weight and height.
- Medical history and information on planned hospitalization (including elective surgery) during the study for medical conditions existing prior to study entry.
- Physical examination including body temperature measured axillary.
- Pregnancy test in females capable of bearing children.
- Blood draw of 10 ml blood for TBE antibody level detection.
- Blood draw of 40 ml blood for cellular immunity.
- Blood draw of 10 ml blood for immune status and quantitative immunoglobulin levels in HSCT patients only.

Subjects who suffer from an acute illness with or without elevated body temperature (\geq 37.5°C, measured axillary with two weeks prior to screening will not be vaccinated. In this case Visit 1 will take place separately at a later date, as long as the study is ongoing.

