11.1 Sample size considerations

For our phase II pilot study a calculation of the sample size was performed using nQuery 6.1. The primary endpoint is the outcome of the NT against 4 weeks after the second vaccination (positive test: Yes/No). Because of deviation of the antibody concentrations from normal distribution (NT level <=10 not detectable indicating a negative test), the outcome is reduced to a binary but clinically more relevant outcome (seroconversion rate: NT levels >10 indicates a positive test). Previously, in a study with heart transplant recipients a seroconversion rate of 35% was detected compared to 100% in the healthy control group [21]. In our study we expect a seroconversion nate of at least 90% in the healthy control group. In the HSCT patients we expect a seroconversion not exceeding 50%. The calculation of the sample size was performed using the following assumption: Significance level alpha 0.05, Power 0.8, ratio of HSCT patients/healthy volunteers: 1/1. With a total number of 46 participants (23 HSCT patients and 23 healthy volunteers) the assumed difference in the seroconversion rate between groups can be detected (using a two-sided Fisher's Exact Test) with 80% Power. We added 10% to adjust for potential loss-to-follow-up which results in 26 HSCT patients and 26 healthy volunteers.

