11.3 Endpoints analysis

The primary endpoint (outcome of NT 4 weeks after the second vaccination) will be analysed using Fisher's Exact Test. For the seroconversion rates, 95% confidence intervals will be calculated. All subjects with available antibody responses fulfilling the eligibility criteria will be included in the analysis

The secondary endpoints (NT 4 weeks after the third vaccination, ELISA prior to the first vaccination and 4 weeks after the second and third vaccination, cellular immunity, immunoglobulin levels and immune reconstitution) will be analysed using descriptive statistics.

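### The primary seroconversion rate counts NT >10 after dose 2 with no baseline NT condition, so antibody present before dose 1 is credited to the vaccine

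*Combined protocol and SAP*

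**What the plan says.** Section 8.5.4.1 sets out to assess immunogenicity of the vaccination by counting "the number of subjects with NT titers against TBE virus >10" four weeks after dose 2. Section 11.1 gives that count its name: "seroconversion rate: NT levels >10 indicates a positive test". The synopsis uses the same label. None of the three places mentions a pre-vaccination titre or a rise from one.

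The analysis set in 11.3 is: "All subjects with available antibody responses fulfilling the eligibility criteria will be included in the analysis". No criterion in 7.1.2 or 7.1.3 uses an antibody result.

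Baseline serum exists. Section 7 says "Serum samples for determination of antibody levels will be obtained immediately before the first (study visit 1", and the screening visit in 8.5.2.1 lists "Blood draw of 10 ml blood for TBE antibody level detection". Section 8.5.3.1 says that for antibody levels "both NT and enzyme linked immunosorbent assay (ELISA) will be performed", which can be read as covering NT on this sample. But the only baseline antibody result in 11.3 is the descriptive secondary "ELISA prior to the first vaccination and 4 weeks after the second and third vaccination". The NT change endpoint in 8.5.4.2 compares post-dose 3 with post-dose 2, not with baseline.

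**The concern.** Seroconversion means moving from negative to positive. An endpoint that looks only at the later titre measures the proportion above the threshold, whatever put them there. If some subjects are above 10 before dose 1, the plan counts them as converted, and no other planned analysis separates them out.

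The two groups are not equally exposed to this. Controls must have had no TBE vaccination (7.1.2). For HSCT recipients, section 7.1 records when TBE vaccination was given before transplant and asks for sibling donors' vaccination status, and section 8.4 supports primary vaccination whatever the pre-transplant history. Carried-over antibody would therefore raise the HSCT rate and narrow the tested difference. Two things are at stake: the HSCT response attributed to the vaccine, and the power of the primary comparison. Protection status is not at stake, because a baseline-positive patient still above 10 at Visit 4 does meet the surrogate.

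**Working it through.** **Inputs from section 11.1.** HSCT rate 50% (stated as an upper bound), control rate 90% (stated as a lower bound), two-sided Fisher's exact test, alpha 0.05, power 0.80, ratio 1:1, 23 per group raised to 26 for 10% loss. The heart-transplant rate is 35%.

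**Assumptions not in the documents.** f is the fraction of HSCT recipients with NT >10 before dose 1. I assume they are still above 10 at Visit 4 and that controls have none. The range of f is illustrative.

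**Step 1, the plan's own figure.** Exact power by full enumeration of the two binomials, 50% vs 90%: 22 per group 78.6%, 23 per group 81.1%, 26 per group 85.5%. So 23 is the smallest size from which 80% is reached, and 23/0.9 = 25.6, rounded up to 26. The sample size reproduces.

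**Step 2, reading (a): 50% is already the overall NT >10 rate.** Power is unchanged. Expected HSCT responders are 26 × 0.5 = 13, of whom 26f were positive before dose 1. The rate in baseline-negatives is (0.5 − f)/(1 − f).

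| f | positive before dose 1 | share of 13 | rate in baseline-negatives |
|---|---|---|---|
| 5% | 1.3 | 10% | 0.45/0.95 = 47% |
| 10% | 2.6 | 20% | 0.40/0.90 = 44% |
| 20% | 5.2 | 40% | 0.30/0.80 = 38% |

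**Step 3, reading (b): 50% is the rate in baseline-negatives.** Observed rate = f + (1 − f) × 0.5, tested against 90%.

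| f | observed HSCT rate | power, 26 per group | power, 23 per group |
|---|---|---|---|
| 0 | 50% | 85.5% | 81.1% |
| 5% | 52.5% | 80.6% | 76.1% |
| 10% | 55% | 75.0% | 70.5% |
| 20% | 60% | 61.6% | 57.5% |

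**Step 4, reading (c): the rate in baseline-negatives is 35%.** At f = 20% the observed rate is 0.20 + 0.80 × 0.35 = 48%, with power 88.8% at 26 per group. Power holds, but the rate is overstated by 13 points. The planned 50% bound is passed only when f exceeds (0.50 − 0.35)/(1 − 0.35) = 0.15/0.65 = 23%.

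**Step 5, cost of restricting to baseline-negatives.** With 50% vs 90% and 26 controls:

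| f | baseline-negative HSCT recipients of 26 | power |
|---|---|---|
| 10% | 23 | 85.5% |
| 20% | 21 | 83.9% |
| 30% | 18 | 83.4% |

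Treating the number of negatives as binomial instead of fixed gives 86.5%, 84.4% and 82.0%.

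**The case against.** The strongest reply is that the harm is not shown. Section 5.1 says protective immunity is lost after allogeneic HSCT and that transfer from the donor does not prevent this. No document gives a non-zero f. In reading (b) with 26 per group, power drops below 80% only somewhere above f = 5%; reading (a) loses none. The bias also runs against finding a difference, so it cannot manufacture a claim that recipients respond less well. All of this stands, and it limits the size of the problem. It does not supply the missing check: section 5.1 is general background, and the plan never tests it on the primary assay.

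A second reply is that NT >10 is a sound protection endpoint, so the fault is one of wording. That is partly right, and the endpoint is worth keeping under its proper name. But 8.5.4.1 uses it to judge the immunogenicity of the vaccination, which is a claim about cause.

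A third reply is that eligibility deals with it. One bullet in 7.1.3, read literally, excludes any history of TBE infection or vaccination. That reading conflicts with the separate bullet limited to vaccination after HSCT, with the synopsis, and with sections 7.1 and 8.4. It is also a criterion on history, not titre, so it would miss donor-derived antibody or unrecognised infection. Baseline ELISA may show antibody descriptively, but section 5.1 notes that it picks up cross-reactive, non-neutralizing antibody, and it is not tied to the primary analysis.

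Finally, restricting to baseline-negatives narrows the population and removes subjects mainly from one group. That is a real cost. With 23 evaluable per group before restriction, power would be 81.7%, 80.7% and 77.8% for f = 10%, 20% and 30%. Section 7.1.5 replaces dropouts before week 8, so 26 is the more relevant starting number. A pre-specified sensitivity analysis avoids changing the primary population.

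**Conclusion.** The concern holds and should be fixed. The primary endpoint carries no baseline condition, baseline NT enters no planned analysis, and any subject above 10 before dose 1 would be counted as a vaccine response. This is certain from the text.

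The size is not known and may be near zero. The power loss depends on f and on whether the planned 50% refers to all recipients or to baseline-negatives. At f = 10% and 26 per group, power is either unchanged at 85.5%, with 20% of HSCT responders misattributed, or falls to 75.0%. These figures also assume that baseline positives stay above 10 at Visit 4 and that no control is positive at baseline.

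**What to change.** 1. State in 8.5.3.1 that NT is run on the pre-vaccination serum, and list baseline NT in 11.3.
2. Define seroconversion as NT ≤10 at baseline and >10 at Visit 4, analysed in baseline-negative subjects with the same Fisher's exact test. Make this the primary analysis or, at minimum, a pre-specified sensitivity analysis of the primary comparison.
3. Report NT >10 at Visit 4 regardless of baseline as seroprotection, and correct the label in the synopsis and 11.1.
4. List baseline-positive subjects separately with their change in titre.
5. Reconcile the synopsis and sections 7.1, 7.1.3 and 8.4 on TBE vaccination before HSCT.

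The cost is protocol wording and one NT per subject on a sample already drawn. The seroconversion denominator shrinks by the number of baseline positives. From 26 enrolled per group, this leaves power above 80% up to f = 30%. If nobody is positive at baseline, the results do not change and the attribution to the vaccine is documented.

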8.5.4.2 Secondary study end points

The secondary end points of this study are:

- Antibody concentrations of TBE ELISA (validated in-house test, Department of Virology, Medical University of Vienna) before and four weeks after the second and third vaccination.
 - Increase of antibody response.
 - Number of subjects with seroconversion defined when patients reach antibody levels above the cut-off of TBE ELISA.
- Antibody concentrations of NT titers four weeks after the third vaccination compared to four weeks after the second vaccination.
 - Increase of antibody response.
 - \circ Number of subjects with NT titers against TBE virus >10.
- Evaluation of cellular immunity prior to and one week after the second and third vaccination.
 - Lymphoproliferative response after vaccination induced by TBE antigen.
 - Increase in cytokine levels induced by TBE antigen

• Evaluation of immune reconstitution and quantitative immunoglobulin levels before first and third vaccination and 12 weeks after first vaccination in HSCT recipients only.

9. SAFETY DEFINITIONS AND REPORTING REQUIREMENTS

9.1 Adverse events (AEs)

9.1.1 Summary of known and potential risks of the study drug

The following side effects have to be considered:

- very common (>1/10): local reactions at the site of injection, transient redness, and swelling.

- common (>1/100;<1/10): systemic reactions including fever, fatigue, headache, muscular pain, arthralgia. These side-effects usually occur within 72 hours after the vaccination, abate within 1-2 days, but do not acquire any medical treatment. All adverse events will be listed in the study documents and have to evaluated by the investigator for causality to the vaccination. After venous puncture local reactions, a hematoma or phlebitis can occur. However, the planed venous punctures withdraw only minor volumes of blood and do not impair the patient's health.

9.1.2 Definition of adverse events

An AE is any untoward adverse change from the subject's baseline condition, i.e., any unfavorable and unintended sign including an abnormal laboratory finding, symptom or disease which is considered to be clinically relevant by the physician that occurs during the course of the study, whether or not considered related to the study drug.

Adverse events include:

- Exacerbation of a pre-existing disease.
- Increase in frequency or intensity of a pre-existing episodic disease or medical condition.
- Disease or medical condition detected or diagnosed after study drug administration even though it may have been present prior to the start of the study.
- Continuous persistent disease or symptoms present at baseline that worsen following the start of the study.
- Lack of efficacy in the acute treatment of a life-threatening disease.
- Events considered by the investigator to be related to study-mandated procedures.

- Abnormal assessments, e.g., ECG and physical examination findings, must be reported as AEs if they represent a clinically significant finding that was not present at baseline or worsened during the course of the study.
- Laboratory test abnormalities must be reported as AEs if they represent a clinically significant finding, symptomatic or not, which was not present at baseline or worsened during the course of the study or led to dose reduction, interruption or permanent discontinuation of study drug.

Adverse events do not include:

- Pre-planned interventions or occurrence of endpoints specified in the study protocol are not considered AE's, if not defined otherwise (eg.as a result of overdose)
- Medical or surgical procedure, e.g., surgery, endoscopy, tooth extraction, transfusion.
 However, the event leading to the procedure is an AE. If this event is serious, the procedure must be described in the SAE narrative.
- Pre-existing disease or medical condition that does not worsen.
- Situations in which an adverse change did not occur, e.g., hospitalizations for cosmetic elective surgery or for social and/or convenience reasons.
- Overdose of either study drug or concomitant medication without any signs or symptoms. However, overdose must be mentioned in the Study Drug Log.

